# 5.0 STUDY PROCEDURES

### Schedule of visits and procedures

An overview of the study visit and procedures schedule is presented in table 1. All participants will be instructed to avoid altering their level of habitual physical activity during the trial. Participants who qualify and agree to P MRS will receive an additional study visit at UWMC lasting 1-2hrs at baseline and after each treatment arm. Presented below is additional information on visit-specific study procedures. Detailed instructions to guide and standardize all study procedures will be provided in the section titled study procedures/sample collection below.

### Screening visit/practice bicycle visit

The screening visit will take place within 28days of the baseline visit. Some components of the initial screening visit may be performed by telephone or in combination with other study visits in order to best accommodate participants' schedules. The screening visit will occur at the prevention center. Study coordinators will obtain informed consent prior to any data acquisition or sample collection

### Screening visit procedures:

- Verification of inclusion and exclusion criteria as outline in sections 3.1 & 3.2 including
- Vital signs and anthropometrics
- 6-minute walk: Participants able to walk 500 meters or more during 6 minutes will be excluded from the study
- *Screening labs (if 6 minute walk <500meters or less):* A renal panel & Complete blood count (CBC)
- Bicycle ergometry practice: The exercise trainer will help familiarize the participant with the bicycle to mitigate significant training effects due to lack of exposure to the equipment
- Questionnaires will be handed out to be returned at the baseline visit. Participants may also choose to complete these at the baseline or online via RedCap ITHS
  - Medical History Questionnaire
  - o Kansas City Cardiomyopathy Questionnaire

Eligibility for the study will be at the discretion of the principal investigator or study clinician after review of the pertinent labs and inclusion/exclusion criteria.

### Baseline visit

The baseline visit will be the same as visits 2-4 with an additional of medical history and anthropomorphic testing. Subject will undergo a baseline evaluation including a detailed assessment of demographics, smoking history, medical history, medication inventory, vital signs and anthropometrics (height, weight, waist to hip ratio). A pregnancy test will be performed on all women of childbearing potential. If the subjects meet the eligibility criteria the study coordinator will contact the subjects' primary physician regarding the subjects' involvement in the trial.

The study drug dispensed at Baseline visit and Visits 2, 3, 4. The participant will receive either placebo or NR or Coenzyme Q10 from the Investigational Drug Service (IDS) and instructed on how to appropriately administer the medications. He or she will be instructed to take the medication daily starting on the day after the study visit.

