# 4.3 Adherence Assessment

Adherence to the study treatment will be assessed by study coordinator phone call midway through each treatment arm to assess adherence and inventory method to assess remaining medication/placebo at the end of the study. Adherence will be defined as consumption of at least 75% of the prescribed regimen. Up to 36 participants may be recruited to compensate for non-adherence or drop-out with the goal of 10 individuals completing in each treatment arm. Participants will be asked to bring in unused study drugs at each visit to return to IDS.

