# Baseline visit and Post-treatment visits (2, 3, 4)

The participant will have been required to fast for at least 6 hrs prior to each visit and abstain from caffeine or smoking before bicycle ergometry testing. Patient should avoid exercise 48hours prior to cycle ergometry. Treatment will be dispensed after cycle

ergometry at baseline and post-treatment visits 2,3 and 4. The following data will be obtained:

- Vital signs.
- Fasting blood collection for banked plasma and peripheral blood mitochondrial energetics.
- Anthropometrics (height and weight and waist to hip ratio)
- Urine pregnancy test will be given to women of child-bearing potential
- Resting energy expenditure (REE) and cycle ergometry will be performed at the Prevention center.
- The optional MRS and Muscle Fatigue tests will occur at the diagnostic imaging center at UWMC at baseline and in the same week of visits 2, 3 and 4 while patient remains on study drug. Patient should wait avoid heavy exercise for 48hrs before MRS.
- Questionnaires will be administered (PROMIS fatigue short form 17, PROMIS physical function short form 20a, and Kansas city heart failure questionnaire)

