### **Procedures/Sample collection:**

An overview of the study visit and procedures schedule is presented in Appendix I. Presented below is additional information on visit-specific study procedures and Table 4.

*Physiologic measurements from cycle ergometry:* The main outcome of this study is aerobic capacity (VO2max) using cycle ergometry. Secondary outcome is muscle performance using measures of total work and work efficiency which will be obtained by cycle ergometry using standard protocol measuring oxygen uptake starting at 0 watts (W) at 60 rotations per minute (rpm) increasing by 30W every 3 minutes until volitional exhaustion adapting a prior protocol used in CKD patients. Approximately 30W of activity is required for grocery shopping and 60W is necessary for household chores. Work efficiency will be calculated as the work performed/energy expended (VO2) above that in cycling 0 watts x 100%. The minimum criteria for a successful efficiency calculation will be a rating of perceived exertion (RPE) of 13 (scale 6-20) or 75% of predicted maximal heartrate. The minimum goal for successfully achieving a VO2max is a RPE of 17 or respiratory exchange ratio≥1. Recovery will consist of pedaling 5 minutes at 10 watts and 60rpm. **Participants should be fasting for at least 6 hrs prior to this test and not exercise for 48hr prior to this test.** 

*PBMC mitochondrial bioenergetic stress test:* Monocytes are specifically selected due the strong correlation of their bioenergetics properties with skeletal muscle and cardiac bioenergetics in the primate model. Blood samples will be process using an established protocol. Sample collection should be coordinated in advance with [name] ([contact]).

*Blood testing for metabolic response profile* (oxidative stress, inflammation, and plasma amino acids, metabolites, and electrolytes). Oxidative Stress and Inflammatory Biomarkers include: C-reactive protein and IL-6 levels will be determined using the automated Abbott FLX C-Reactive Protein Assay and by ELISA, respectively. Plasma

F2-isoprostanes and isofurans will be measured by GC-MS as described by Roberts and Morrow at Vanderbilt University (c/o [name]: [contact]).

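### Applied at visits 2 and 3, the first-dose rule removes the 1-week washout; visit 4 dispensing is surplus; and the MRS window overlaps both the washout and the first baseline dose

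*Combined protocol and SAP*

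**What the plan says.** **Dispensing and first dose.** Section 5.0, *Baseline visit*, describes dispensing for the whole trial: "The study drug dispensed at Baseline visit and Visits 2, 3, 4". The same paragraph then gives the first-dose rule: "He or she will be instructed to take the medication daily starting on the day after the study visit". It makes no exception for a washout. The section opens by saying that "The baseline visit will be the same as visits 2-4", apart from some added history and measurements. The following section repeats that treatment is handed out after "ergometry at baseline and post-treatment visits 2,3 and 4".

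**Washout and periods.** *Washout (week 7 and 14)* places one week between a visit and the next product. Table 1 starts the second and third periods in weeks 8 and 15. Section 7.1 repeats the 1-week washout, and Section 7.6.1 rests the no-carryover assumption on it together with the length of treatment. Table 1 marks dispensing at baseline, visit 2 and visit 3 only. Table 2 in Section 7.3 shows three periods in every sequence.

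**MRS.** Follow-up MRS and muscle fatigue tests are to be done "in the same week of visits 2, 3 and 4 while patient remains on study drug". The rest rule is "Patient should wait avoid heavy exercise for 48hrs before MRS". *Optional Procedures* allows testing within 3 days either side of each visit, from baseline to visit 4, in a subset of 20. Each of these visits includes ergometry with the load "increasing by 30W every 3 minutes until volitional exhaustion". Section 4.3 adds: "Participants will be asked to bring in unused study drugs at each visit to return to IDS". No section states the day of the last dose relative to the visit or the scan.

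**The concern.** The day-after rule sits under a baseline heading, but its paragraph names the later dispensing visits. A coordinator handing out the second or third supply could reasonably give the same instruction. Participants would then start the next product in the week that the schedule reserves for washout.

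The visit 4 entry tells staff to dispense when nothing remains to be dispensed.

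The MRS instructions raise a separate question. A scan after a follow-up visit may fall in the washout, yet it is meant to be on drug. A scan after the baseline visit may fall after dosing has begun, yet it is meant to be a baseline. Correcting the dosing sentence alone would settle neither.

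At stake are one consistent start date for each product and a known drug status for each scan.

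**Working it through.** **1. Reproduce the plan's schedule.** Inputs: 6-week periods (Section 4.1, Table 1) and a 1-week washout. Visit at the end of period k falls in week 6k + (k − 1):
- k = 1: 6
- k = 2: 12 + 1 = 13
- k = 3: 18 + 2 = 20

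This matches the plan's weeks 6, 13 and 20.

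**2. Convert to days,** with day 1 the first dose of period 1.

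| | Drug days | Visit | Washout |
|---|---|---|---|
| Period 1 | 1–42 | visit 2, day 42 | 43–49 |
| Period 2 | 50–91 | visit 3, day 91 | 92–98 |
| Period 3 | 99–140 | visit 4, day 140 | none |

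**3. Apply the day-after rule at visits 2 and 3.** First doses fall on 42 + 1 = day 43 and 91 + 1 = day 92, the first days of weeks 7 and 14. The differences are 50 − 43 = 7 and 99 − 92 = 7. Drug-free days are 0 instead of 7 at each of two transitions.

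**4. What would follow.**
- Visits held at weeks 6, 13 and 20: exposure is 42, 91 − 42 = 49 and 140 − 91 = 49 days. The allowed range is 42 ± 7, or 35 to 49, so the 49-day periods would pass a window check.
- Each period held at 6 weeks: visits fall at weeks 6, 12 and 18, and visit 4 is 2 weeks early, outside its 7-day window. The third product would then start on 84 + 1 = day 85, not day 92.
- Time from the last dose of one product to the next outcome visit is 91 − 42 = 49 days as planned, 49 days in the first case, and 84 − 42 = 42 days in the second.

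**5. Period length.** Section 2.3 gives 56-day phases and Section 7.6.1 about two months. With 56 days, the second product would start on day 56 + 7 + 1 = 64 as planned or day 57 under the day-after rule, again 7 days apart. The conflict does not depend on which length is right.

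**6. Dispensing count.** Three periods need three supplies. Table 1 has three; the text has four.

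**7. Follow-up MRS.** The window −3 to +3 has 7 days, of which 3 follow the visit. Using visit 2 (day 42):

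| Scan day | 48 h after ergometry? | If dosing stops at the visit | If dosing continues to the scan and day 50 is kept | If 7 drug-free days are kept |
|---|---|---|---|---|
| +1 (day 43) | no | off drug | 50 − 43 − 1 = 6 drug-free days | next start day 51 |
| +2 (day 44) | possible | off drug | 50 − 44 − 1 = 5 | day 52 |
| +3 (day 45) | possible | off drug | 50 − 45 − 1 = 4 | day 53 |

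On days −3 to 0 the scan is on drug and the 7-day washout is untouched.

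**8. Baseline MRS.** The first dose is on day +1 after the baseline visit. A post-visit scan that respects the 48-hour rest falls on day +2 or +3, after dosing has begun.

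**9. Scans that could be affected.** Follow-up: 0 to 20 × 3 = 60. Baseline: 0 to 20. The documents do not show where in the window scans would fall. *Optional Procedures* also numbers the scan visits as baseline, 2, 4 and 6; visits 2, 3 and 4 are used here, as in Table 1.

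**The case against.** The best defence of the dosing sentence is its place. It stands under *Baseline visit*, speaks of one study visit, and four other places in the protocol give the washout. The statement that baseline matches visits 2 to 4 introduces visit content, not dosing. This stands as evidence of intent: a reader might infer that the trial was designed without a washout, and the documents rule that out. It does not remove the ambiguity, because the paragraph lists the later dispensing visits and makes no exception for them.

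On MRS, a reader might infer that a post-visit scan cannot be on study drug. The documents do not show that:
- The last-dose day is not stated, and Section 5.0 expressly wants the scan on drug.
- Section 4.1 provides a spare week for scheduling problems.
- Sections 2.3 and 5.0 and Table 1 call MRS a visit, so returning unused product there would fit Section 4.3.
- Days −3 to 0, 4 of the 7 permitted days, raise no conflict over drug status.

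A reader might also infer that a scan 2 or 3 days after the last dose no longer reflects treatment. Section 7.6.1 calls the half-lives short but gives no figure, and it mentions residual effects up to 3 weeks. What remains is an unstated last-dose day and a window that overlaps the washout.

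Finally, MRS is optional and listed under exploratory endpoints, although the text there also calls it secondary. That limits the weight of this part.

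**Conclusion.** The point holds as an inconsistency in operative instructions, of minor severity. The day-after rule, applied at visits 2 and 3, removes all 7 washout days at both transitions. Visit 4 dispensing contradicts Table 1 and the three-period design. The MRS window permits follow-up scans in the washout and a baseline scan after the first dose.

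The expected effect on the VO2max comparison is small. The washout section and Table 1 make the intended start clear. Even without a washout, at least 42 days would separate the last dose of one product from the next outcome visit, against the 3 weeks of residual effect that Section 7.6.1 allows.

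The day numbers assume 6-week periods and visits on their nominal days. The off-drug status of post-visit scans further assumes that dosing stops at the visit, which the washout section and Section 4.3 suggest but do not state.

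**What to change.** 1. **First dose.** Limit the day-after rule to the baseline supply. State that the supplies given at visits 2 and 3 are first taken after 7 drug-free days counted from the actual last dose, nominally at the start of weeks 8 and 15.
2. **Visit 4.** Delete it from both dispensing sentences in Section 5.0.
3. **Last dose.** State that the last dose of each period is taken on the visit day.
4. **Follow-up MRS and muscle fatigue tests.** Schedule them on days −3 to 0, on the current product, and before ergometry if on the same day. Days −3 or −2 are preferable: ergometry also requires 48 hours without exercise, and the protocol does not say whether the fatigue test counts as exercise.
5. **Baseline MRS.** Do it before the first dose.

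The alternative is to continue the current product until a post-visit scan and start the washout then. It can preserve 7 drug-free days, but participants would go home with two blinded supplies, and the next start would move by up to 3 days. Scanning before the visit avoids both.

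The cost is revised protocol and participant instructions and a narrower scheduling window, 4 days instead of 7 (2 if days −3 and −2 are used), for an optional measure in up to 20 participants. Visit weeks, sample size and analysis do not change, and no extra product is needed.

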# Baseline visit and Post-treatment visits (2, 3, 4)

The participant will have been required to fast for at least 6 hrs prior to each visit and abstain from caffeine or smoking before bicycle ergometry testing. Patient should avoid exercise 48hours prior to cycle ergometry. Treatment will be dispensed after cycle

ergometry at baseline and post-treatment visits 2,3 and 4. The following data will be obtained:

- Vital signs.
- Fasting blood collection for banked plasma and peripheral blood mitochondrial energetics.
- Anthropometrics (height and weight and waist to hip ratio)
- Urine pregnancy test will be given to women of child-bearing potential
- Resting energy expenditure (REE) and cycle ergometry will be performed at the Prevention center.
- The optional MRS and Muscle Fatigue tests will occur at the diagnostic imaging center at UWMC at baseline and in the same week of visits 2, 3 and 4 while patient remains on study drug. Patient should wait avoid heavy exercise for 48hrs before MRS.
- Questionnaires will be administered (PROMIS fatigue short form 17, PROMIS physical function short form 20a, and Kansas city heart failure questionnaire)

### **Procedures/Sample collection:**

An overview of the study visit and procedures schedule is presented in Appendix I. Presented below is additional information on visit-specific study procedures and Table 4.

*Physiologic measurements from cycle ergometry:* The main outcome of this study is aerobic capacity (VO2max) using cycle ergometry. Secondary outcome is muscle performance using measures of total work and work efficiency which will be obtained by cycle ergometry using standard protocol measuring oxygen uptake starting at 0 watts (W) at 60 rotations per minute (rpm) increasing by 30W every 3 minutes until volitional exhaustion adapting a prior protocol used in CKD patients. Approximately 30W of activity is required for grocery shopping and 60W is necessary for household chores. Work efficiency will be calculated as the work performed/energy expended (VO2) above that in cycling 0 watts x 100%. The minimum criteria for a successful efficiency calculation will be a rating of perceived exertion (RPE) of 13 (scale 6-20) or 75% of predicted maximal heartrate. The minimum goal for successfully achieving a VO2max is a RPE of 17 or respiratory exchange ratio≥1. Recovery will consist of pedaling 5 minutes at 10 watts and 60rpm. **Participants should be fasting for at least 6 hrs prior to this test and not exercise for 48hr prior to this test.** 

*PBMC mitochondrial bioenergetic stress test:* Monocytes are specifically selected due the strong correlation of their bioenergetics properties with skeletal muscle and cardiac bioenergetics in the primate model. Blood samples will be process using an established protocol. Sample collection should be coordinated in advance with [name] ([contact]).

*Blood testing for metabolic response profile* (oxidative stress, inflammation, and plasma amino acids, metabolites, and electrolytes). Oxidative Stress and Inflammatory Biomarkers include: C-reactive protein and IL-6 levels will be determined using the automated Abbott FLX C-Reactive Protein Assay and by ELISA, respectively. Plasma

F2-isoprostanes and isofurans will be measured by GC-MS as described by Roberts and Morrow at Vanderbilt University (c/o [name]: [contact]).

# Blood Collection:

- NAD samples will be obtained from fasting whole blood collected in one 2.7ml Blue (sodium citrate tube). From the blue tube, after inversion mixing, 0.5ml will be pipetted into 2 cryotubes **on dry ice.** Samples will be immediately frozen on dry ice and placed in -80C ASAP. Samples will be sent to [name] in clinical pharmacology ([contact]).
- EDTA Plasma samples will be sent to University of California at Davis West Coast Metabolomics for liquid chromatography high-resolution mass spectrometry (LC-MS) for targeted metabolomics analysis. We will perform additional transcriptomics using mRNA samples obtained from Paxgene tubes which will also be sent to West Coast Metabolomics.
- Paxgene mRNA will be obtained at baseline and post-intervention visits.
- Clinical laboratory assays for determination of comprehensive metabolic panel (electrolytes, blood urea nitrogen, creatinine, glucose, albumin, total protein, calcium, alkaline phosphatase, ALT, AST, total bilirubin), CPK, lactate, triglyceride will be performed at the *KRI Core Research laboratory*.

*Urine collection:* **Spot urine** for metabolomics will be collected at baseline and after each treatment period (visits 2-4).

# Mid-intervention visits/phone calls:

All subjects will receive a phone call by study coordinators 4 weeks (mid-way) into each intervention arm to confirm patients are taking their treatment/placebo medication in order to ensure adherence. They will also receive a reminder of their subsequent visits.

# Week 6, 13, 20 (Visit 2, 3, 4):

The prevention center and [name] lab will be contacted to arrange the primary outcome of resting energy expenditure, aerobic capacity and secondary outcomes of monocyte mitochondrial energetics at the end of each treatment period. Patients will also have fasting blood collection and return a 24hr urine collection. If qualified, they will also receive a repeat MRS at UWMC during the same week. **Patient remain on treatment during these visits to ensure drug effect.** 

# Washout (week 7 and 14):

After the second visit, the participant will undergo a 1 week washout period prior to initiating the subsequent treatment arm for another 6 week period.

# **Optional Procedures:**

A subset of participants (N=20) may choose to undergo the following muscle imaging procedures. Subjects will go to the UW DISC lab for testing +/-3 days from each scheduled visit (Baseline – visit 4).

*Magnetic Resonance Spectroscopy:* Leg MRS will serve as a secondary outcome and optional. All participants will be offered the option to receiving leg MRS. As mentioned above, only 4 MRS will be obtained as part of this study (at Baseline, visit 2, 4 and 6). MRS will be used to measure phosphorylation capacity (ATPmax) tibialis anterior leg skeletal muscle. These functional tests assist to perturb the cell physiological state in order to measure the contents and dynamics of key metabolic compounds important in mitochondrial energy flux. P MRS is reliable with a documented coefficient of variation for oxidative phosphorylation of 5.1% and has a strong correlation with V02max. Scheduling of this test should be coordinated with [name] ([contact]).

*Muscle Fatigue:* We will test muscle fatigability at each follow-up visit. We will test the TA (tibialis anterior) leg muscle and determine the isometric force generated at 70% of maximal voluntary contraction (MVC) against a force transducer. Using labview software to measure and record the force-time waveform of each contraction we will initiate the protocol at 50 contractions per minute at 70% MVC for one minute. At each 1 minute increment will increase the contraction rate by 10 contractions per minute and reassess the subjects relative perceived exertion on a scale of 1-10 until the patient can no longer maintain the contraction waveform.

				Treatment arm 1 (6wk +/-7d)	Treatment arm 2 (6wk +/-7d)	Treatment arm 3 (6wk +/-7d)
	Screen Day -28	Baseline	Optional MRS visit	Day 1 Visit 2 Week 6 (+/-7d)	Wk 8 Visit 3 Week 13 (+/-7d)	Wk 15 Visit 4 Week 20 (+/-7d)
Time	1-1.5hr	3hr	1-2hr	3hr	3hr	3hr
Location	PC	PC	UWMC	PC	PC	PC
Compensation	\$10	\$50	\$50	\$100	\$100	\$100
Consent	Х					
Practice bicycle	Х					
Screeninglabs	Х					
Medical history		Х				
Medicine inventory		Х				
Vital signs/Anthro	Х	Х		Х	Х	Х
Product dispensed		Х		Х	Х	
Assess AEs				Х	Х	Х
Bicycle Vo2max/work		Х		Х	Х	X
REE		Х		Х	Х	Х
PBMC bioenergetics**		Х		Х	Х	Х
31P MRS (subgroup)*			Х	X (UWMC)	X (UWMC)	X (UWMC
mRNA (paxgene)		Х		Х	Х	X
Blood		Х		Х	Х	X
Urine		Х		Х	Х	X
Drug level/NAD		Х		Х	Х	X
PROMIS Fatigue/PF PRO	landout	Х		Х	Х	Х

